#### 8.1.2 Secondary Endpoints

- Any cause death within 30 days or neurological death within 12 months  $\pm$  8 weeks.
- Number of Barrel® VRD treated aneurysms achieving Raymond Grade I or II at 12 months  $\pm$  8 weeks in the absence of retreatment, parent artery stenosis ( $> 50\%$ ), or target aneurysm rupture.
- Number and percentage of successful device implants
- Angiographic evidence of in-stent stenosis at 12 months  $\pm$  8 weeks reported according to the following ordinal groups:  $<25\%$ ,  $25-50\%$ ,  $51-75\%$ ,  $>75\%$ .
- Device-related Serious Adverse Events (SAEs).
- The composite percentage of patients with modified Rankin Score of 0-2 or no change from

baseline at 12 months  $\pm$  8 weeks.

## 9. Trial Population

### 9.1 Number of Patients

A maximum of 159 subjects will be enrolled (consented) into the study at up to 28 centers to ensure the study has an adequate number of treated subjects; up to 119. The duration of the study participation is 12 months  $\pm$  8 weeks and the total expected study duration, including completion of all follow-up requirements, is approximately 2.5 years.

### 9.2 Patient Inclusion Criteria

A subject who meets all of the following criteria may be included in the trial:

1. Male or female between 18 and 85 years old.
2. A wide-neck aneurysm with a neck  $\geq$  4mm or a dome-to-neck ratio  $<$  2, that is also a bifurcating or branch MCA or basilar aneurysm and de novo or non-de novo MCA or basilar aneurysm where no stent was utilized.
3. Subject's aneurysm arises from a parent vessel with a diameter  $\geq$  2mm and  $\leq$  4mm.
4. Appropriate informed consent obtainable as determined by local IRB.
5. Life expectancy  $>$  24 months.

### 9.3 Patient Exclusion Criteria

A subject who meets any of the following criteria will not be included in the trial:

1. Aneurysm rupture within 30 days of enrollment.
2. MCA or basilar bifurcating aneurysms not treatable with coiling.
3. Subject with anatomy not accessible for Barrel VRD treatment.
4. Aneurysm neck  $>$  8 mm.
5. Subject presents with an intracranial mass or is currently undergoing radiation therapy for carcinoma of the head or neck region.
6. Subject has additional aneurysms for which treatment is planned within 18 months.
7. Subject has platelet count of  $<$ 70,000.
8. Subject has had a previous intracranial stenting procedure associated with the target aneurysm.
9. Subject has an International Normalized Ratio (INR)  $\geq$  1.7 or is on one of the following anti-coagulant/anti-platelet medications: Aggrenox, Cilostazol, Apixaban, Dabigatran, Fondaparinux, Lepirudin, Pradaxa, Rivaroxaban, Argatroban, Arixtra.
10. Subject has serum creatinine level  $>$  2mg/dl at baseline screening.
11. Subject has known allergies to nickel-titanium metal.
12. Subject has known allergies to aspirin or heparin.
13. Subject has a life-threatening allergy to contrast (unless treatment for allergy can be tolerated).
14. Subject has a known cardiac disorder, likely to be associated with cardioembolic symptoms such as atrial fibrillation (AFIB).
15. Subject has any condition, which in the opinion of the treating physician, would place the subject at a high risk of embolic stroke.
16. Subject is currently participating in another clinical research study.
17. Subject is pregnant or breastfeeding.

18. Subject has participated in a drug study within the last 30 days.
19. Subject cannot or is unwilling to take ASA and a P2Y12 Platelet Inhibitor as required by the protocol following the procedure.
20. Subject is unable or unwilling to comply with protocol requirements and obtain required clinical evaluations and follow-up.

Before any subject is enrolled in the study, the baseline angiogram will be reviewed by a Barrel expert to ensure that the target intracranial aneurysm (IA) is amenable to treatment with the Barrel VRD device.

## 10. Device Descriptions

The Barrel® VRD features a self-expanding design that allows it to be completely deployed and fully retrieved.

The Barrel® VRD is comprised of nitinol and several platinum marker bands. The proximal marker band attaches to a wire that pushes the device through a commercially available 0.021” microcatheter to the intended treatment site. The delivery wire detaches from the Barrel® VRD by electrolytic means after deployment with the Reverse Medical® Detachment System (Model ED2-RM-VRD).

The Barrel® VRD is packaged as a single unit with the detachable delivery wire and introducer sheath. The system is provided sterile, non-pyrogenic, and is intended for single use only. The Barrel® VRD is not commercially available and is considered investigational in this study. The Barrel® VRD and components are required to be used per the protocol and as specified in the IDE Instructions for Use (IFU) document.

The Reverse Medical® Detachment System is a battery-operated device designed to initiate and control detachment of Reverse Medical® detachable implants within the vasculature. The Reverse Medical® Detachment System is designed for multiple uses, but the battery must be removed and the unit cleaned after each procedure. A new battery should always be inserted into the Detachment Box before each procedure.

[figure not shown]
The Reverse Medical® Detachment System is designed to apply a constant current and detect System detachment. It maintains a current by sensing the amount of resistance to current flow and adjusting the voltage required to maintain a constant current.

The Reverse Medical® Detachment System is designed to identify the changes in voltage required by the System associated with detachment. Once detachment is identified, the Detachment System indicates detachment with an audible and visual “Detach” signal and stops the flow of current to the System.

[figure not shown]
A Reverse Medical Cable Set – 275 cm length (Model RMCS – 2.75VRD) is provided sterile and is for single use only. The cable set connects to the Detachment Box through a bayonet type dual pin connector that ensures correct polarity. The Reverse Medical Cable Set and Detachment Box will be provided at no charge separately. One 9-volt battery and a sterile needle (20 G or 22 G) will also be needed for the embolization procedure.

The Barrel® VRD is specifically designed for use with the Reverse Medical® Detachment System and Cable Set. This Reverse Medical® Detachment System will be provided separately. The Barrel® VRD and Detachment System are depicted in Figures 10-1 through 10-4 and Table 10-1.

**Figure 10-1 Detachment Zone and Delivery Wire of Barrel® VRD**

**Figure 10-2 Image of Actual Barrel® VRD**

**Table 10-1 Materials Used in the Barrel® VRD**

Nitinol Wire (Heat treated, Laser Cut, Electropolished)
Platinum Wire
Steel, Stainless 301
Solder
Sheath, Polypropylene
Urethane Adhesive
Cyanoacrylate Adhesive
Platinum Marker band
Urethane Adhesive

**Figure 10-3 Cable Set**

Item	Description / Material
1	Clip - ABS plastic, copper wire
2	Cable – copper wire, silicone jacket insulation (2.75M in length)
3	Connector - ABS plastic, copper wire

**Figure 10-4 Reverse Medical Detachment Box**

## **11. Study Materials**

### **11.1 Instructions for Use**

Instructions for the delivery and release of the Barrel® Vascular Reconstruction Device are outlined in the Barrel® VRD Instructions For Use (IFU) and the Reverse Medical® Detachment System IFU.

### **11.2 Device Accountability**

Investigators will be provided with sterile investigational products including Barrel® VRDs, Cable Sets, and Detachment Boxes. Complete accountability for each device must be maintained. Any unused devices must be returned to the Sponsor at the conclusion of the study or upon product expiration.

## **12. Study Methods and Procedures**

### **12.1 Enrollment Procedures**

Prospective patients, as defined by the inclusion and exclusion criteria, will be considered for enrollment in this trial. Enrollment will be considered the point of consent. Prior to enrolling a patient, it must be verified that all criteria are met. Patients must meet **all** of the inclusion criteria and **none** of the exclusion criteria prior to treatment in the study.

### **12.2 Informed Consent**

This protocol requires written informed consent, in accordance with applicable federal, state, and study center regulations. This consent shall be obtained from each patient, or appropriate surrogate, prior to the investigational procedure. The Investigator will retain a copy of the signed informed consent document in each subject's record, and provide a copy to the subject. The Investigator shall not request the written informed consent of any patient, and shall not allow any patient to participate in the study before obtaining Institutional Review Board (IRB) approval.

Prior to starting the study, the Investigator will provide Medtronic with a copy of the Informed Consent Document approved by the IRB with documented evidence that the protocol has received IRB approval.

### **12.3 Physician Training**

Physicians who participate in this study will be trained using a phantom or bench-top model of the Barrel® VRD under fluoroscopic visualization.

### **12.4 Schedule of Events**

The tests and evaluations to be conducted at baseline, procedurally, and during follow-up are summarized in the Table 12-1.

**Table 12-1 Schedule of Tests**

Tests and Evaluations	Screening/ Baseline	Procedural (Day 0)	30 days ±14 days	180 days ±30 days	12 months ±8 weeks	Unscheduled Visit
Inclusion/Exclusion	X					
Demographics	X					
Medical history	X					
Medications	X	X	X	X	X	X
Blood Labs	X					
Modified Rankin Score	X		X	X	X	
NIHSS Score	X			X	X	X 
Adverse Events		X	X	X	X	X
Angiography 	X 	X		X 	X	
Raymond Grade Scale	X 	X		X	X	

MRA is acceptable if performed according to the standard of practice at the participating institution.

The baseline angiogram must be taken no more than 180 calendar days prior to the procedure.

For previously coiled aneurysms

If an angiogram is performed as standard patient care it should be sent to the core laboratory for analysis.

If visit is related to target aneurysm or potentially associated adverse event

## 12.5 Procedure

Access the targeted vessel and perform an angiogram using standard technique. Advance the Barrel® VRD through a 0.021 microcatheter to the desired position and deploy the device utilizing the delivery wire. Detach the delivery wire from the Barrel® VRD using the Reverse Medical® Detachment System and remove the microcatheter from the subject.

Use the following steps to administer coils:

- a. Use a guidewire and microcatheter to access the aneurysm through the device's struts.
- b. After the microcatheter has been positioned within the aneurysm, detachable embolization coils can be deposited into the aneurysm per manufacturer's instructions.
- c. Warning – Observe the VRD's marker position during the coiling procedure to ensure the VRD does not migrate from detached position.
- d. After placement of the last coil, verify the VRD has remained patent and properly positioned.
- e. Carefully remove the microcatheter from the VRD's struts.

## 12.6 Study Evaluations

### 12.6.1 Screening/Baseline Evaluations

The following information will be collected:

- Inclusion/Exclusion Criteria
- Demographics
- Medical History
- Medications
- Modified Rankin Score
- NIHSS Score
- Angiography data
- Raymond Grade for previously coiled aneurysms

All medications that a patient is taking starting 30 days prior to screening will be collected and followed for the duration of the study. In addition, the following medications will be collected throughout the study: antithrombotic, antiplatelet, anticoagulant, inhibitor of ADP-induced platelet aggregation, all medications administered during the study procedure, and medications associated with adverse events.

### 12.6.2 Procedural Evaluations

During the operative procedure the following information will be recorded:

- Devices and components used (Barrel® VRD, guidewires, and delivery catheters) including manufacturer and model number
- Puncture time
- Detachment time
- Location of aneurysm
- Coiling packing density
- Device implant success (yes/no), defined as the ability to implant the device in the target area
- Stenosis in the parent artery
- Intra-operative complications
- Presence of vasospasms (time of onset, vessels involved, time resolved). Vasospasm will be recorded as an AE only if it led to a subsequent thrombotic or ischemic event.
- Medications

### 12.6.3 Immediate Post-operative Evaluations

The following information will be recorded during the immediate post-operative evaluation:

- Angiographic assessment
  - Stenosis
  - Raymond Grade

Class 1: Complete occlusion - complete obliteration of the aneurysm.

Class 2: Residual neck - persistence of any portion of the original defect of the arterial wall as seen on any single projection, but without opacification of the aneurysmal sac.

Class 3: Residual aneurysm - opacification of the aneurysmal sac.

- Description of adverse events
- Medications

### 12.6.4 Post-placement Antiplatelet Agents

Antiplatelet agents will be given after the Barrel device placement procedure as defined below:

- Aspirin: At least 81 mg daily for a minimum of 12 months
- P2Y12 Platelet Inhibitor: Daily for a minimum of 3 months

Medications could be continued beyond above regimen if medically indicated.

### 12.6.5 Follow-Up (30-day, 180-day, and 12-month)

The following assessment will be completed at the specified time points below. All visits should be completed by study subjects with successful implant of the Barrel VRD. Subjects that underwent attempted delivery with the Barrel VRD, but were not implanted should complete the 30-day visit and be exited from the study.

- 30 Day  $\pm$  14 Days
  - Neurologic Evaluation
    - The Investigator is responsible for ensuring that the administration of the modified Rankin Score is conducted by a trained person with appropriate qualifications to perform these evaluations.
  - Details of any additional (subsequent) procedures or additional treatments
  - Description of adverse events, including the time of onset
  - Medication Usage
  - 30 day evaluations may be performed remotely via telephone if subject is not available for a visit to the study center.

- 180 Day  $\pm$  30 days
  - Neurologic Evaluation
    - The Investigator is responsible for ensuring that the administration of the NIHSS and modified Rankin Score are conducted by a trained person with appropriate qualifications to perform these evaluations.
  - Details of any additional (subsequent) procedures or additional treatments
  - Angiographic assessment (if done as standard of care)
    - Stenosis
    - Raymond grade
  - Description of adverse events, including the time of onset
  - Medication Usage
- 12 month  $\pm$  60 days
  - Neurologic Evaluation
    - The Investigator is responsible for ensuring that the administration of the NIHSS and modified Rankin Score are conducted by a trained person with appropriate qualifications to perform these evaluations.
  - Details of any additional (subsequent) procedures or additional treatments
  - Angiographic assessment
    - Stenosis
    - Raymond grade
  - Description of adverse events, including the time of onset
  - Medication Usage

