**Table 3-1 Schedule of Tests**

Tests and Evaluations	Screening/ Baseline	Procedural (Day 0)	30 days ±14 days	180 days ±30 days	12 months ±8 weeks	Unscheduled Visit
Inclusion/Exclusion	X					
Demographics	X					
Medical history	X					
Medications	X	X	X	X	X	X
Blood Labs	X					
Modified Rankin Score	X		X	X	X	
NIHSS Score	X			X	X	X 
Adverse Events		X	X	X	X	X
Angiography 	X 	X		X 	X	
Raymond Grade Scale	X 	X		X	X	

MRA is acceptable if performed according to the standard of practice at the participating institution.

The baseline angiogram must be taken no more than 180 calendar days prior to the procedure.

For previously coiled aneurysms

If an angiogram is performed as standard patient care it should be sent to the core laboratory for analysis.

If visit is related to target aneurysm or potentially associated adverse event

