### 6.5 Statistical Analysis Sets

The primary analysis set will be based on the intention-to-treat (ITT) population set. For this study, all subjects who meet the study entry criteria, sign the written informed consent (enrolled), and undergo attempted delivery with the Barrel VRD will be counted in the primary analysis set of ITT.

Analysis will also be performed on the per-protocol population set, defined as all subjects included in the ITT population set who have complied with the protocol without major protocol deviations, and have completed the 12-month angiographic evaluation.

The primary analyses for both the safety and effectiveness endpoints will be based on the observed data.

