### **12.6.7 Study Exit**

Upon completion of the specified study follow-up at 12 months the subject will be exempt from further data collection. The subject will be seen by the treating physician according to standard care following intracranial aneurysm treatment. If the subject underwent attempted delivery with the Barrel VRD but did not receive a Barrel VRD implant, the subject will be exited from the study following the 30 day visit.

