## 12.8 Adverse Event Reporting

All adverse events will be collected during the course of the study on the eCRFs.

Adverse event status will be evaluated throughout the study. These will include events occurring from the point of consent until a subject exits the study. Investigators must obtain all information available to determine the causality and outcome of the AE and to assess whether it meets the criteria for classification as a serious and/or unexpected event requiring notification to the Sponsor, regulatory agency, and as applicable, IRB/EC, within the specified reporting timeframe. AEs will be categorized using the definitions in **Section 12.8.1**.

All study AEs, as well as the treatment and follow-up required, should be documented in the subject's medical records and in the eCRF. All study AEs will be followed by the Investigator until resolution or until the end of the 12 month follow-up. A list of potential anticipated adverse events is provided in **Section 13**.

All relevant medical conditions reported at screening/baseline visit will be recorded in the medical history form, including any signs and symptoms related to the condition of intra-cranial aneurysm.

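### Subjects without an implant exit at a 30-day visit that may fall as early as day 16, so up to 14 days of the 30-day death endpoint can go unobserved for them

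*Protocol*

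**What the plan says.** - **Exit rule.** Section 12.6.5: "Subjects that underwent attempted delivery with the Barrel VRD, but were not implanted should complete the 30-day visit and be exited from the study". Section 12.6.7 says of the same subjects that "the subject will be exited from the study following the 30 day visit", and Section 12.6.8.2 repeats the rule. In all three places exit is tied to the visit, not to a calendar day.
- **Visit window.** Tables 3-1 and 12-1 give "30 days ±14 days", with the procedure as Day 0. Section 12.6.5 repeats the window and allows a telephone contact when the subject cannot come to the centre.
- **End of collection.** Section 12.8 on adverse events: "These will include events occurring from the point of consent until a subject exits the study". The same section adds: "All study AEs will be followed by the Investigator until resolution or until the end of the 12 month follow-up".
- **Endpoint.** Section 8.1.2 lists first among the secondary endpoints: "Any cause death within 30 days or neurological death within 12 months".
- **Analysis set.** Under Section 6.5, eligible, consented subjects who "undergo attempted delivery with the Barrel VRD will be counted in the primary analysis set of ITT". An implant is not required.
- **Purpose.** Section 4.1 gives adequate safety follow-up of subjects who receive no implant as the reason for keeping them to the 30-day visit.

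**The concern.** The endpoint has a fixed 30-day horizon, but the exit rule follows a visit that may take place up to two weeks before that horizon. For implanted subjects an early visit does no harm, because the 180-day and 12-month visits will bring to light a death or event later in the first month. Non-implanted subjects have no later visit. Nowhere does the protocol ask for vital status or serious adverse events at day 30 once a subject has exited.

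What is at stake is the completeness of 30-day death, and of early safety events generally, in subjects who were exposed to an attempted device delivery. Events lost in this way can only lower the observed count. An analysis rule written later cannot recover data that were never collected.

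**Working it through.** **Inputs.** Window 30 ± 14 days and procedure on Day 0 (Tables 3-1 and 12-1); exit at the 30-day visit (Sections 12.6.5, 12.6.7, 12.6.8.2); collection until exit (Section 12.8); 119 treated subjects (Section 6.3). The protocol gives no implant-failure rate. The endpoint names no starting point; I count its 30 days from the procedure.

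**1. The window.** 30 − 14 = day 16 and 30 + 14 = day 44, which is 44 − 16 + 1 = 29 permitted days.

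**2. Days unobserved for a non-implanted subject seen on day v.** Unobserved = max(0, 30 − v).

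| Visit day v | Unobserved days of the 30 |
|---|---|
| 16 | 14 (days 17 to 30) |
| 23 | 7 |
| 29 | 1 |
| 30 to 44 | 0 |

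**3. How much of the window is early.** Days 16 to 29 are 14 of the 29 permitted days (48%). The other 15 (52%) lose nothing.

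**4. Average loss if visits are spread evenly over the window (assumption).** The sum of 30 − v over days 16 to 29 is 14 + 13 + … + 1 = 105. Over all visits the mean is 105/29 = 3.6 days. Among early visits it is 105/14 = 7.5 days.

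**5. Number of subjects affected (assumed non-implant rate, visits evenly spread).**

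| Assumed rate | Non-implanted, of 119 | Seen before day 30 (× 14/29) |
|---|---|---|
| 2% | 2.4 | 1.1 |
| 5% | 6.0 | 2.9 |
| 10% | 11.9 | 5.7 |
| 15% | 17.9 | 8.6 |

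This gives about 1 to 9 subjects.

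**6. Effect on the reported rate.** One missed death is 1/119 = 0.84 percentage points.

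**7. Expected size, as an illustration.** Assume 6 to 12 non-implanted subjects and a 30-day mortality of 5% spread evenly over the 30 days; neither figure is in the protocol.
- Visits evenly spread: 6 × 0.05 × 3.62/30 = 0.04 to 12 × 0.05 × 3.62/30 = 0.07 missed deaths.
- Every visit on day 16: 6 × 0.05 × 14/30 = 0.14 to 12 × 0.05 × 14/30 = 0.28 missed deaths.
- Divided by 119, this is about 0.03 to 0.24 percentage points.

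**8. Design figures.** The sample size rests on the 12-month occlusion endpoint and uses none of these quantities. Section 6.7 analyses secondary endpoints descriptively.

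**The case against.** The best case against acting is that the gap is narrow and partly covered. More than half of the permitted visit days lose nothing, the average loss is under four days if visits are evenly spread, and the endpoint carries no test or threshold. Section 12.8 also has investigators follow recorded adverse events to resolution or to the end of the 12-month follow-up. A complication already noted at an early visit that later proves fatal should therefore still be picked up, and Section 12.8.3 asks for documents on deaths. All of this stands. It confines the loss mainly to events that begin after an early exit, and makes the expected effect small. It does not close the gap, because a compliant site may still stop looking before day 30.

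A reader might infer more than the documents support:
- *That days 17 to 30 are lost for every non-implanted subject.* This is so only for a visit on day 16.
- *That a subject who exits early is counted as alive at day 30.* The protocol does not say whether such a subject is counted as event-free or as missing, and that may be settled in a SAP that is not shown.
- *That the visit window causes the conflict with the adverse-event follow-up rule.* Exit with an unresolved event sits badly with that rule whether the visit is on day 16, 30 or 44. The two passages need reconciling, but this is a separate matter.
- *That these subjects are at especially high early risk, or that device-related events will be materially under-counted.* The protocol has no figure for the first. On the second, Section 12.8.1 requires a strong temporal relationship to the device, which a new event after an early exit in a subject without an implant would less readily meet.

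It is also fair to say that the same exit rule leaves these ITT subjects with no planned visit for the rest of the 12-month safety period. The change proposed here does not address that.

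**Conclusion.** The point holds in limited form. The exit rule, the visit window and the end of adverse-event collection together let a non-implanted ITT subject leave observation up to 14 days before the 30-day death endpoint closes. Thirty-day deaths and early safety events may therefore be under-ascertained, and any such loss lowers the observed count.

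The size is small: roughly 1 to 9 subjects exiting early if 2% to 15% of 119 are not implanted and visits fall evenly across the window, and 0.84 percentage points for each death missed. Both the non-implant rate and the spread of visits are assumptions. So is counting the 30 days from the procedure; if they ran from consent, which comes earlier, the gap would be no larger. Nothing in the primary efficacy test, its power, its alpha or the sample size is touched. The change is worth making because it is cheap and the data cannot be recovered afterwards.

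**What to change.** In Tables 3-1 and 12-1 and in Sections 12.6.5, 12.6.7 and 12.6.8.2, state that for a subject with attempted delivery but no implant the exit contact takes place on day 30 to day 44, by telephone if needed, and that vital status and adverse events are recorded through at least day 30. The ± 14-day window can stay as it is for implanted subjects. The largest possible unobserved stretch of the 30 days then falls from 14 days to 0 for subjects whose contact is made.

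Separately, reconcile the exit rule with the Section 12.8 statement on following adverse events, so that it is clear what happens to an event still open when a non-implanted subject exits.

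The cost is a sentence in each of these places and the loss of the early half of the visit window for a few subjects. No new visit is needed, since the telephone contact is already allowed.
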